#### **Events NOT meeting the AE definition**

- Any clinically significant abnormal laboratory findings or other abnormal safety assessments which are associated with the underlying disease, unless judged by the Investigator to be more severe than expected for the participant’s condition.

- The disease/disorder being studied or expected progression, signs, or symptoms of the disease/disorder being studied, unless more severe than expected for the participant's condition.
- Medical or surgical procedure (eg, endoscopy, appendectomy): the condition that leads to the procedure is the AE.
- Situations in which an untoward medical occurrence did not occur (social and/or convenience admission to a hospital).
- Anticipated day-to-day fluctuations of pre-existing disease(s) or condition(s) present or detected at the start of the study that do not worsen

### **10.3.2 Definition of SAE**

If an event is not an AE per definition above, then it cannot be an SAE even if serious conditions are met (eg, hospitalization for signs/symptoms of the disease under study, death due to progression of disease).

**A SAE is defined as any untoward medical occurrence that, at any dose:**

- a) Results in death**
- b) Is life-threatening**

The term “life-threatening” in the definition of “serious” refers to an event in which the participant was at risk of death at the time of the event. It does not refer to an event, which hypothetically might have caused death, if it were more severe.

- c) Requires “a new” inpatient hospitalization or prolongation of existing hospitalization**

In general, hospitalization signifies that the participant has been detained (usually involving at least an overnight stay) at the hospital or emergency ward for observation and/or treatment that would not have been appropriate in the physician's office or outpatient setting. Complications that occur during hospitalization are AEs. If a complication prolongs hospitalization or fulfills any other serious criteria, the event is serious. When in doubt as to whether “hospitalization” occurred or was necessary, the AE should be considered serious.

Hospitalization for elective treatment of a pre-existing condition that did not worsen from baseline is not considered an AE.

- d) Results in persistent disability/incapacity**

- The term disability means a substantial disruption of a person's ability to conduct normal life functions.
- This definition is not intended to include experiences of relatively minor medical significance such as uncomplicated headache, nausea, vomiting, diarrhea, influenza, and accidental trauma (eg, sprained ankle) which may interfere with or prevent everyday life functions but do not constitute a substantial disruption.

- e) Is a congenital anomaly/birth defect**

**f) Other situations:**

- Medical or scientific judgment should be exercised in deciding whether SAE reporting is appropriate in other situations such as important medical events that may not be immediately life-threatening or result in death or hospitalization but may jeopardize the participant or may require medical or surgical intervention to prevent one of the other outcomes listed in the above definition. These events should usually be considered serious.

Note: The following list of medically important events is intended to serve as a guideline for determining which condition has to be considered as a medically important event. The list is not intended to be exhaustive:

- Intensive treatment in an emergency room or at home for:
  - Allergic bronchospasm
  - Blood dyscrasias (ie, agranulocytosis, aplastic anemia, bone marrow aplasia, myelodysplasia, pancytopenia, etc),
  - Convulsions (seizures, epilepsy, epileptic fit, absence, etc).
- Development of drug dependence or drug abuse
- ALT  $>3 \times$  ULN + total bilirubin  $>2 \times$  ULN or asymptomatic ALT increase  $>10 \times$  ULN
- Suicide attempt or any event suggestive of suicidality
- Syncope, loss of consciousness (except if documented as a consequence of blood sampling)
- Bullous cutaneous eruptions
- Cancers diagnosed during the study or aggravated during the study
- Chronic neurodegenerative diseases (newly diagnosed) or aggravated during the study

**10.3.2.1 Recording and follow-up of AE and/or SAE**

**AE and SAE recording**

- When an AE/SAE occurs, it is the responsibility of the Investigator to review all documentation (eg, hospital progress notes, laboratory reports, and diagnostics reports) related to the event.
- The Investigator will then record all relevant AE/SAE information in the CRF.
- It is **not** acceptable for the Investigator to send photocopies of the participant's medical records to the Sponsor or Representative in lieu of completion of the AE/SAE CRF page.
- There may be instances when copies of medical records for certain cases are requested by the Sponsor or Representative. In this case, all participant identifiers, with the exception of the participant number, will be redacted on the copies of the medical records before submission to the Sponsor or Representative.

- The Investigator will attempt to establish a diagnosis of the event based on signs, symptoms, and/or other clinical information. Whenever possible, the diagnosis (not the individual signs/symptoms) will be documented as the AE/SAE.

### Assessment of intensity

The severity of neutropenia, hypersensitivity, and infusion related reactions will be graded using the NCI-CTCAE v3 (see [Table 12](#), [Table 13](#), [Table 14](#)).

**Table 12 - Grading of infusion related reactions (NCI-CTCAE v3)**

Grade	Description
1	Mild reaction; infusion interruption not indicated; intervention not indicated
2	Requires therapy or infusion interruption but responds promptly to symptomatic treatment (eg, antihistamines, NSAIDS, narcotics, IV fluids); prophylactic medications indicated for $\leq 24$ hrs
3	Prolonged (ie, not rapidly responsive to symptomatic medication and/or brief interruption of infusion); recurrence of symptoms following initial improvement; hospitalization indicated for other clinical sequelae (eg, renal impairment, pulmonary infiltrates)
4	Life-threatening; pressor or ventilatory support indicated
5	Death

**Table 13 - Grading of hypersensitivity reactions (NCI-CTCAE v3)**

Grade	Description
1	Transient flushing or rash; drug fever
2	Rash; flushing; urticaria; dyspnea; drug fever $\geq 38^{\circ}\text{C}$ ( $\geq 100.4^{\circ}\text{F}$ )
3	Symptomatic bronchospasm, with or without urticaria; parenteral medication(s) indicated; allergy-related edema/angioedema; hypotension
4	Anaphylaxis
5	Death

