### **Secondary Endpoints (Safety)**

The safety endpoints are:

- Incidence of serious adverse events
- The incidence of major or opportunistic bacterial or fungal infections
- The incidence of major or opportunistic bacterial or fungal infections in patients with grade 4 neutropenia
- The incidence of hypersensitivity reactions, infusion reactions, gastrointestinal perforation
- White cell count, hemoglobin, platelets, creatinine, total bilirubin, ALT on days 1, 4, 7, 15, 21, 29 (if still hospitalized)

---

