### 8.3.6 Adverse event of special interest

#### Adverse event of special interest

An adverse event of special interest (AESI) is an AE (serious or nonserious) of scientific and medical concern specific to the Sponsor's product or program, for which ongoing monitoring and immediate notification by the Investigator to the Sponsor is required. Such events may require further investigation in order to characterize and understand them. Adverse events of special interest may be added, modified or removed during a study by protocol amendment.

The AESI require reporting to the sponsor (or designee) within 24 hours of learning of the event:

- **Adverse Events of Special Interest (AESI; serious and nonserious) include the following:**
  - Grade  $\geq 2$  infusion related reactions (Infusion related reactions are defined as any signs or symptoms experienced by patients who receive IMP within 24 hours of the start of infusion)
  - Grade  $\geq 2$  hypersensitivity reactions
  - Grade 4 neutropenia ( $ANC < 500/\text{mm}^3$ )
  - Grade 4 neutropenia with concurrent invasive infection ( $ANC < 500/\text{mm}^3$ )
  - Increase in alanine transaminase (ALT)  $\geq 3X \text{ ULN}$  (for patients with normal baseline) or  $> 3X \text{ ULN}$  AND at least 2-fold increase from baseline value (for patients with abnormal baseline)
  - Invasive bacterial or fungal infections of clinical significance with confirmed diagnosis based on the Investigator's assessment with appropriate diagnostic workups and consultations
  - Symptomatic overdose (serious or nonserious) with IMP
    - An overdose (accidental or intentional) with the IMP is an event suspected by the Investigator or spontaneously notified by the participant (not based on systematic pills count) and defined as an increase of at least 30% of the dose to be administered in the specified duration or if the dose is administered in less than half the recommended duration of administration.

Management of acute reactions is described in [Section 10.3.4](#).

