2.1.4.1 Adverse events variables

Adverse event observation period

- Pre-treatment AEs are AEs that developed or worsened or became serious from the signed informed consent date up to first administration of IMP
- TEAEs are AEs that developed or worsened or became serious during the TEAE period
- Post-treatment AEs are AEs that developed or worsened or became serious during the post-treatment period

All AEs (including SAEs and AESIs) will be coded to a “LLT”, “PT”, “HLT”, “HLGT”, and associated primary “SOC” using the version of MedDRA currently in effect at Sanofi at the time of database lock.

The occurrence of AEs (including SAEs and AESIs) will be recorded from the time of signed informed consent until the end of the study.

Adverse events of special interest (AESI; serious and nonserious) include the following:

- Grade ≥ 2 infusion related reactions (Infusion related reactions are defined as any signs or symptoms experienced by patients who receive IMP within 24 hours of the start of infusion)
- Grade ≥ 2 hypersensitivity reactions
- Grade 4 neutropenia ($ANC < 500/mm^3$)

- Grade 4 neutropenia with concurrent invasive infection (ANC<500/mm³)
- Increase in alanine transaminase (ALT) $\geq 3X$ ULN (for patients with normal baseline) or $>3X$ ULN AND at least 2-fold increase from baseline value (for patients with abnormal baseline)
- Invasive bacterial or fungal infections of clinical significance with confirmed diagnosis based on the Investigator's assessment with appropriate diagnostic workups and consultations
- Symptomatic overdose (serious or nonserious) with IMP
 - An overdose (accidental or intentional) with the IMP is an event suspected by the Investigator or spontaneously notified by the participant (not based on systematic pills count) and defined as an increase of at least 30% of the dose to be administered in the specified duration or if the dose is administered in less than half the recommended duration of administration.

AESIs will be flagged in the database using search criteria. All AEs captured on the general AE form, the ALT increase form, infusion reaction symptoms form, and the infection event form will be searched. The list of search criteria is provided in [Appendix C](#).

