2.4.5.7 Analyses of anti-sarilumab antibodies

The following summary will be provided separately for ADA positive patient, ADA negative patient.

ADA prevalence and titer

The following summary will be provided based on the ADA population:

- Number (%) of patients with an ADA positive sample at baseline
 - The summary statistics (including number, median, Q1, Q3, minimum and maximum) of the titer for the baseline ADA positive patients
- Number (%) of patients with an ADA negative sample at baseline

ADA incidence and titer

The following summary will be provided based on the ADA population during TEAE period:

- Number (%) of ADA-negative patients
- Number (%) of ADA-positive patients
 - The summary statistics (including number, median, Q1, Q3, minimum, and maximum) of the peak post-baseline titer for all ADA-positive patients
- Number (%) of treatment-emergent ADA-positive patients.

- The summary statistics (including number, median, Q1, Q3, minimum, and maximum) of the peak post-baseline titer for treatment-emergent ADA-positive patients
- Number (%) of treatment-boosted ADA positive patients.
- The summary statistics (including number, median, Q1, Q3, minimum, and maximum) of the peak post-baseline titer for all treatment-boosted ADA-positive patients

In addition, number (%) of patients with ADA positive or negative response at each visit will be summarized by treatment group.

Plot of percentage of patients with treatment-emergent ADA positive response at each visit will be provided by treatment group.

Listing for ADA status will also be provided.

ADA and PK

Descriptive summary of sarilumab concentrations in serum will be provided by ADA patient classifications (positive or negative) over time for the sarilumab treatment group by number of sarilumab doses.

ADA and clinical efficacy

The primary and key secondary efficacy endpoints will be analyzed by ADA patient classifications (positive or negative).

ADA and clinical safety

The safety assessment will focus on the following events:

- Hypersensitivity (standardized MedDRA query (SMQ): Hypersensitivity [Narrow])
- Anaphylaxis (SMQ: Anaphylaxis [Narrow])
- IV infusion reaction (HLT: IV infusion reaction)
- TEAEs leading to permanent treatment discontinuations

Number (%) of patients with these events will be summarized by ADA patient classifications (positive or negative) for the sarilumab treatment group.

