Appendix C AEsIs and search criteria

Table 5 – AEsIs and search criteria

AESI flag	Search^a criteria
Grade ≥2 infusion related reactions	Any Grade ≥2 (moderate) TEAE of infusion related reactions within 24 hours from the start of study drug infusion based upon CRF checkbox: Infusion Reaction and Yes to AESI event and Severity Grade ≥2.
Grade ≥2 hypersensitivity reactions	SMQ: Anaphylactic reaction, Hypersensitivity or Angioedema and Grade ≥2 (moderate)
Grade 4 neutropenia	ANC <500/mm ³ and CRF checkbox: Yes to AESI event
Grade 4 neutropenia with concurrent invasive infection ^b	ANC <500/mm ³ and Primary SOC: Infections and infestations within 1 week of ANC <500/mm ³
Invasive bacterial or fungal infection ^c	Primary SOC: Infections and infestations
Alanine transaminase (ALT) increase	CRF checkbox: ALT Increase and Yes to AESI event
Overdose ^d	CRF checkbox: Symptomatic overdose

TEAE: Treatment-emergent adverse event

a All SMQs are narrow search

b Patients having both a Grade 4 Neutropenia and a concurrent infection event will be further reviewed by the medical team to confirm that the infection event is invasive.

c Patients identified as having an infection event will be further reviewed by the medical team to confirm that the infection is invasive.

d Standard AESI applies to all Sanofi studies

Signature Page for VV-CLIN-0581573 v3.0
efc16844-16-1-9-sap

Approve & eSign	[Redacted] Clinical [Redacted]
-----------------	--------------------------------------

Approve & eSign	[Redacted] [Redacted]
-----------------	--------------------------

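### SAP Appendix C flags Grade ≥2 hypersensitivity by narrow-SMQ terms alone, so a reaction that a site reported as a hypersensitivity AESI can be missed in that count

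*Protocol*

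**What the plan says.** **Reporting and grading (protocol).** Section 8.3.6 lists Grade ≥2 hypersensitivity reactions among the AESIs and states: "The AESI require reporting to the sponsor (or designee) within 24 hours of learning of the event". Section 10.3.2.1 sets the scale: "The severity of neutropenia, hypersensitivity, and infusion related reactions will be graded using the NCI-CTCAE v3". Grade 2 in Table 13 covers "Rash; flushing; urticaria; dyspnea; drug fever", with a 38 °C threshold for the fever. Table 2 makes the event a secondary safety endpoint, "The incidence of hypersensitivity reactions, infusion reactions, gastrointestinal perforation", with no grade limit. The safety objectives in Table 1 name Grade ≥2 hypersensitivity.

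**Counting (SAP).** Section 2.1.4.1 says "AESIs will be flagged in the database using search criteria". The hypersensitivity row of Appendix C, Table 5 is "SMQ: Anaphylactic reaction, Hypersensitivity or Angioedema and Grade ≥2 (moderate"), and footnote a adds "All SMQs are narrow search". Section 2.4.5.1 tabulates AESIs by these groupings. It adds separate TEAE summaries for infusion reactions, ALT increase and infections, but not for hypersensitivity.

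**ADA table (SAP 2.4.5.7).** Infusion reactions are identified here as "IV infusion reaction (HLT: IV infusion reaction"), whereas Appendix C identifies them by a CRF checkbox.

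**The concern.** The site and the analysis use different tests for the same AESI. The site applies clinical judgment: it decides that a reaction is hypersensitivity, grades it and reports it. The analysis asks whether the coded term belongs to one of three narrow SMQs. If the site wrote down a sign and that sign codes outside those SMQs, an event reported as a hypersensitivity AESI is absent from the hypersensitivity AESI row, and nothing in the SAP brings it back.

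That row is the only by-arm grouped count of hypersensitivity that the SAP specifies, so it will in practice supply the incidence for the secondary safety endpoint. AESI imbalance is also among the criteria in protocol 7.2 and 9.6 for discontinuing an arm.

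The ADA table raises a smaller point of the same kind. One event type, infusion reactions, has two counting rules in one SAP, so two tables could show different patients under similar labels.

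**Working it through.** The plan gives no expected rate of hypersensitivity and no figure to reproduce. The check is a comparison of rules, followed by an illustration.

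**1. The seven rows of Appendix C**

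| AESI row | Coded term or lab search | CRF checkbox | Medical review |
|---|---|---|---|
| Infusion related reaction, Grade ≥2 | No | Yes, with AESI tick | No |
| Hypersensitivity, Grade ≥2 | Three narrow SMQs | No | No |
| Grade 4 neutropenia | ANC | Yes (AESI tick) | No |
| Grade 4 neutropenia with invasive infection | ANC and SOC | No | Yes (footnote b) |
| Invasive bacterial or fungal infection | SOC | No | Yes (footnote c) |
| ALT increase | No | Yes, with AESI tick | No |
| Overdose | No | Yes | No |

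Four rows use the investigator's checkbox and two use a term search followed by medical review. Only hypersensitivity has neither.

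**2. What the row uses and omits.** It searches the reported AE forms (SAP 2.1.4.1) and uses the reported grade. It omits the AESI designation.

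**3. Other routes into the output**
- Protocol 10.3.2.1 asks sites to record a diagnosis in preference to its signs where they can. This reduces sign-only terms but does not rule them out.
- A sign arising within 24 hours of infusion start can be flagged as an infusion reaction if it is Grade ≥2 and ticked. The TEAE period runs to the last dose plus 60 days (SAP 2.1.4), so a later reaction has no such route. An earlier one caught there is still absent from the hypersensitivity row.
- Every TEAE appears in the tables by SOC and PT, and every AE is listed (SAP 2.4.5.1). These keep the event visible but do not give a hypersensitivity incidence.

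**4. Direction.** Let S be the patients with a Grade ≥2 term in the narrow SMQs, and I the patients with a Grade ≥2 event designated by the site as a hypersensitivity AESI. The plan counts |S|. Then

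|S| − |I| = |S not I| − |I not S|.

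The second term is the possible loss described here. The first is a possible gain, because the row does not require an AESI tick and so can flag events that no site designated. The documents fix neither term, so the sign is unknown.

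**5. Illustration (all inputs assumed except n).** Take n = 160, the planned size of a sarilumab arm (protocol 9.2). Assume 8 patients in I, a fraction f of them coded outside the narrow SMQs, and no patients in S outside I. The flagged count is 8 × (1 − f):

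| f | Flagged | Incidence | Clopper-Pearson 95% interval |
|---|---|---|---|
| 0 | 8 | 8/160 = 5.0% | 2.2% to 9.6% |
| 0.25 | 6 | 6/160 = 3.75% | 1.4% to 8.0% |
| 0.50 | 4 | 4/160 = 2.5% | 0.7% to 6.3% |
| 0.75 | 2 | 2/160 = 1.25% | not computed |

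The loss runs from nothing to most of the events, and the documents do not place f within that range.

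**6. Timing.** The log for Amendment 04 (11-Jun-2020) shows that the grading tables were added then. The SAP's version history ends on 05-May-2020, so nothing shows that Appendix C was checked against Table 13.

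**The case against.** Term-based flagging is what the protocol asks for. Section 9.4.3.2.1 says AESIs will be defined by a PT or a prespecified grouping, and a narrow SMQ is such a grouping. It is standardized and does not depend on how readily a site ticks a box. Table 13 only grades severity; it does not say which events are hypersensitivity. A site that reports a hypersensitivity AESI has already made a diagnosis and is asked to record it. Fever and dyspnea are also listed as COVID-19 symptoms in protocol 2.2, so admitting sign-only terms could add noise. The ADA breakdown is descriptive, covers sarilumab patients only and does not claim to reproduce the AESI table.

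Most of this stands. There is no contradiction between protocol and SAP, and the row is a defensible choice. What remains is narrower: an event that a site designated as this AESI can be left out of this AESI's own count, with no reconciliation step, although every other row has investigator input or medical review. The overlap with COVID-19 symptoms also argues for using the investigator's blinded judgment, since a coded term alone cannot separate a drug reaction from the disease.

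A reader might infer that reported reactions do drop out, that the count can only fall, and that the sarilumab-placebo difference is therefore understated. The documents do not support this. They do not give the contents of the SMQs or the HLT, the row can also add events that no site designated, and they do not state that true cases fall mainly on active drug.

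**Conclusion.** The gap is real and small. Appendix C can miss a hypersensitivity AESI that a site reported, if the site recorded a sign and the coded term lies outside the three narrow SMQs. Such an event would be missing from the hypersensitivity count, not from all safety output.

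The number of events affected, and the net effect on the comparison with placebo, cannot be determined from the documents. The 8-of-160 figures are illustration only, and if every report is coded to a narrow term nothing is lost.

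The two rules for infusion reactions in Appendix C and SAP 2.4.5.7 are certain from the text. Whether they select different patients depends on coding content that the documents do not give.

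This is a low-cost improvement to make before database lock. It does not invalidate the safety analysis.

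**What to change.** 1. In Appendix C, change the hypersensitivity row to: (narrow SMQ and Grade ≥2) or (event reported by the investigator as a hypersensitivity AESI and Grade ≥2).
2. Add a blinded medical review of discordant cases, those found by one arm of the rule only. Footnotes b and c already provide medical-team review for infections, though they do not state that it is blinded. Report the discordant cases by arm.
3. In SAP 2.4.5.7, identify infusion reactions by the Appendix C flag, or show that flag beside the HLT, so that the ADA and AESI tables can be reconciled.
4. State how the secondary endpoint, which has no grade limit in protocol Table 2, will be counted.

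The cost is a few lines of SAP text, some programming and a short review. Three other rows already use the AESI tick, but SAP 2.1.4.1 names no hypersensitivity form. Confirm that hypersensitivity designations can be retrieved; if they cannot, take them from the AESI reports that 8.3.6 requires. The downside is that the wider rule may admit a few non-allergic events, such as COVID-19 fever or dyspnea, which the blinded review limits.
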